#### 8.2.3 Analyses of the Secondary Study Endpoints

Secondary endpoints of this study include the following: subjective global assessment, BPH Impact Index, quality of life measure from the IPSS, nocturia item score from the IPSS, peak uroflow, residual volume, prostate specific antigen (PSA) level, erectile and ejaculatory function, ICS*male* Incontinence scale, Jenkins Sleep Dysfunction scale, and the NIH Chronic Prostatitis Index (pain, urinary, and quality of life impact).

Responses for the four questions on the subjective global assessment form are ordinal with lower values reflecting a better outcome. Responses for each of these questions will be transformed to 0 to 100 with higher scores reflecting better outcomes. A similar transformation will be used for the quality of life and nocturia items from the IPSS.

Since each participant will be on each dose level for 24 weeks, longitudinal analyses will be performed on each of the above measures to compare the phytotherapy arm with the placebo arm while accounting for the changes over time (baseline, 24, 48 and 72 weeks). The primary statistical technique that will be used is mixed models repeated measures analysis (in SAS, PROC MIXED will be used). This technique will control for intra-patient variation. The final covariance structure to be used in these models will be selected after all of the data have been collected. A significance level of 0.05 will be assumed for all longitudinal comparisons. Regarding multiple comparisons, differences between the two treatment groups with respect to the changes in the secondary endpoints from baseline to 24 weeks, baseline to 48 weeks, and baseline to 72 weeks will be examined to determine if they are significantly different from zero. If these differences are significantly different from zero, comparisons between specific timepoints (48 weeks versus 24 weeks, 72 weeks versus 48 weeks, and 72 weeks versus 24 weeks) for the secondary endpoints will be performed. The Hochberg step-up method will be used for each set of these multiple comparisons.

The statistical distributions of all of the above measures will be checked for normality. Appropriate transformations will be considered for any measure appearing to have a distribution that deviates greatly from a normal distribution.

Complete blood counts and serum chemistry measurements will be categorized by severity grade from the NCI Common Toxicity Criteria. For each participant and each time period on a dose level (1-24 weeks = level 1, 25-48 weeks = level 2, 49-72 weeks = level 3), the most severe grade of a laboratory level will be taken. For each dose level and laboratory measure, the proportions of participants who have abnormalities of severity grade 3 or greater will be compared between the phytotherapy and placebo arms using Fisher's exact test. A two-sided 0.05 significance level will be used for these comparisons.

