#### 5.2 Retitration and Rechallenge with Study Medications

A participant may experience a symptomatic side effect or other abnormality (e.g., a laboratory abnormality) that either he or the investigator believes may be related to the study medication and require withdrawal. Investigators will consider the possibility of a study medication side effect especially in the event of a new, persistent abnormality in any blood test, particularly one that would have excluded a participant's enrollment at baseline, or in the event of new evidence of myocardial infarction or ischemia on the periodic study EKGs. In these circumstances, it may be prudent to attempt a rechallenge of study medication in order to ascertain more evidence of causality and to better assess severity of the adverse effect. Whether or not to perform a rechallenge is the decision of the site principal investigator; obviously, it would be inadvisable to rechallenge a patient who had a serious reaction with a high likelihood of being related to the study medication.

In the event that there is an interruption of therapy and the participant does not take the study medication for at least 14 days (e.g. due to compliance problems, lost medication, physician stopping drug for mild intolerance or minor adverse event), the participant may be retitrated on the medication.

In the event that the participant experiences a moderate or severe adverse event and it is the physician's medical judgment that the participant should be restarted on the study medication and the physician has contacted the Clinical Review Committee and received approval, the participant may be rechallenged.

Retitration or re-challenge should utilize the same kit of medication that the participant has been using or a new kit for that participant may be issued (contact the Drug Distribution Center to request an additional kit if necessary). The participant should be dosed in the following manner. The participant should start at the lowest dose (1 capsule daily) for at least 1 week (longer if physician/participant desires) and then add 1 capsule per day each week until the previous maximum dose (2 gelcaps/day or 3 gelcaps/day) is

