reached or the participant becomes intolerant of the medication. Investigators may suggest that participants spread doses out over the day to increase tolerability. If, in the medical judgment of the physician (as in the case of a severe adverse event or reaction) medication should not be continued, or in the event that a participant does not want to continue the medication, the medication does not have to be restarted.

It should also be noted that, under the principle of intention-to-treat, even if a participant will no longer continue to take his study medication, he should be encouraged to continue his study visits and all data (with the exception of pill counts) should be collected.

The procedure for re-challenge will vary with the specific clinical situation, but should follow the general guidelines below:

- The date of last study medication use by the participant should be recorded on the study drug administration form. All study medications should be discontinued.
- 2) The site principal investigator should determine if it is safe to re-challenge the participant. If so, re-challenge should be discussed with the participant.
- 3) If the participant agrees, he should remain off study medication until all symptoms or abnormalities have stopped (it may be very useful to create a daily diary for the participant to use during this time). The participant should remain off study medication for at least one additional week (to ensure that there is stability in the absence of the symptoms).
- 4) The participant should be followed closely (at least weekly) for recurrence of the symptoms or abnormalities; he should also be advised to contact study staff if his symptoms recur. Again, it may be useful to continue use of a daily diary for the participant. If symptoms recur after restarting the study medication, the investigator should consider withdrawing the participant permanently from study medication. If the symptoms/abnormalities do not recur, the participant may continue in the study following usual study procedures.

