5) NOTE: If, after withdrawing the study medication, the participant's symptoms/abnormalities do not diminish, the investigator may wish to discuss re-challenge with the participant (since the symptoms may have been due to some cause other than the study medication). Careful monitoring of the participant should be observed during this re-challenge period. When assessing the potential causal relationship between the symptom/abnormality and the study medication, remember that the phytotherapy contains many fat-soluble constituents, so that the participant may have detectable tissue levels for several weeks after the medication is discontinued.

If subjects do not redevelop the side effect on re-challenge, they can remain on the final dose for that phase of the study until they have completed 24 total weeks of therapy at that dose, and then be escalated as called for in the protocol, unless they are already at triple dose, in which case they will be at the end of the study.

If on re-challenge, a participant once again develops the same side effect at a higher dose of study medication, but has tolerated a lower dose, he can be dropped back to the lower, tolerable dose for the rest of the study.

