#### 5.9 Criteria for Study Discontinuation

All participants should be followed for 72 weeks from the date of randomization, and should be encouraged to undergo all protocol procedures. Participants may withdraw from the study at any time.

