#### 8.2.4 Safety Analysis

Adverse event data will be summarized by treatment arm to capture the proportion of participants reporting at least one episode of a specific adverse event (incidence table), incidence of adverse events causing withdrawal, and incidence of serious adverse events. The total number of episodes for each event reported (frequency table), and the severity and attribution to treatment arm of each episode reported within body system (severity and attribution table), will also be displayed by treatment arm. Listings of adverse events by participants and event will also be provided. Comparisons of incidence of each adverse event between treatment and placebo will be performed using the two-group chi-square test, or Fisher's exact test when the assumptions for the chi-square test are not tenable. A two-sided statistical test with a significance level of 0.05 will be used for these analyses. In addition, 95% confidence intervals will be computed for differences in proportions of adverse events between study arms.

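### Laboratory results are labelled by dose from study week although Section 5.2 lets actual dose depart from that calendar, and adverse events are compared only over all 72 weeks, so safety at each dose step is blurred

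*Combined protocol and SAP*

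**What the plan says.** For blood counts and chemistries, Section 8.2.3 takes each man's worst grade within windows defined by study week, "1-24 weeks = level 1, 25-48 weeks = level 2, 49-72 weeks = level 3", and compares the proportions at grade 3 or above between arms by Fisher's exact test, two-sided 0.05, for each dose level. The same section gives the premise for its longitudinal analyses: "Since each participant will be on each dose level for 24 weeks".

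Section 5.2 describes departures from that calendar:
- After a break of at least 14 days, or on re-challenge, capsules are built up again: "The participant should start at the lowest dose (1 capsule daily) for at least 1 week", then one more capsule per day each week.
- A re-challenged man whose side effect does not return can stay on his dose "until they have completed 24 total weeks of therapy at that dose, and then be escalated as called for in the protocol".
- If the side effect returns at a higher dose but a lower one was tolerated, "he can be dropped back to the lower, tolerable dose for the rest of the study".
- For a man who stops drug, "he should be encouraged to continue his study visits and all data (with the exception of pill counts) should be collected".

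Section 5.9 fixes the follow-up clock: "All participants should be followed for 72 weeks from the date of randomization".

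For adverse events, Section 8.2.4 states: "Adverse event data will be summarized by treatment arm to capture the proportion of participants reporting at least one episode". Its tests compare whole arms. Section 6.2 tabulates events by arm and severity grade. Neither section splits them by dose or period.

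**The concern.** Section 1.1 gives the double and triple doses as the reason for the trial and for close toxicity monitoring, and Section 2.1 puts tolerability in the primary objective. A reader will therefore take a row labelled dose level 3 as evidence about the triple dose. Under the calendar rule that row also contains men who were off drug, on a reduced dose, or far enough behind to be still at level 2. If the lower doses are safer, the level 3 rate is diluted.

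For adverse events the issue is different and needs no departure from the dosing calendar. A single 72-week comparison adds 48 weeks of events at lower doses to those at the top dose. It cannot show at which step an excess began.

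**Working it through.** **1. The plan's own safety figure.** Section 8.1 assumes a 2.5% placebo rate, 10% on active, 157 per arm and one-sided 0.05, and states 80% power. The pooled normal formula with continuity correction gives 81.0%, so the figure reproduces. (Exact one-sided Fisher gives 83.5%; the uncorrected normal formula gives 86.7%.) The test in Section 8.2.3 is two-sided Fisher, for which exact power is 74.3%. That is the starting value below. The gap between 80% and 74% comes from the choice of test and has nothing to do with dose labelling.

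**2. Which laboratory results can be mislabelled.** Section 4.3 and Appendix I schedule samples at weeks 12, 24, 36, 48, 60 and 72. The level 2 window holds weeks 36 and 48, and the level 3 window holds weeks 60 and 72. Planned escalation to level 3 follows week 48, and 60 − 48 = 12. A man less than 12 weeks behind has therefore normally reached level 3 by the first scheduled sample in that window; likewise 36 − 24 = 12 for level 2. The results at risk are those from men 12 or more weeks behind, permanently reduced, off drug or in a restart ramp when sampled, and any unscheduled samples.

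**3. Size for laboratory results (illustrative).** The documents give no rate of re-challenge, delay, reduction or stopping, so the share f of the active arm not at level 3 in weeks 49-72 is an assumption. Take 10% at level 3 and 2.5% otherwise:

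apparent rate = (1 − f) × 10% + f × 2.5%

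| f | Apparent level 3 rate | Power, two-sided Fisher, 157 per arm |
|---|---|---|
| 0% | 10.0% | 74.3% |
| 5% | 9.6% | 70.3% |
| 10% | 9.25% | 66.1% |
| 15% | 8.9% | 61.5% |
| 20% | 8.5% | 56.7% |
| 30% | 7.75% | 46.5% |

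**4. Size for adverse events (illustrative).** Assume a 5% background risk per 24-week period in both arms, independence between periods, 175 per arm and two-sided 0.05. Risk over 72 weeks = 1 − the product of (1 − period risk). Placebo: 1 − 0.95³ = 14.3%. Power is Φ[(d − 1.96 × se0)/se1], with d the difference in risk, se0 the pooled and se1 the unpooled standard error.

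Excess at the top dose only (active 5%, 5%, 12%):
- Pooled: active 1 − 0.95² × 0.88 = 20.6%; d = 0.0632, se0 = 0.0405, se1 = 0.0404; (0.0632 − 0.0795)/0.0404 = −0.40; power 34%.
- Last period, 5% against 12%: d = 0.07, se0 = 0.0298, se1 = 0.0296; (0.0700 − 0.0584)/0.0296 = 0.39; power 65%.

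Excess from the first dose onward:
- Active 8%, 10%, 12%: pooled 14.3% against 27.1%, power 85%; last period alone 65%.
- Active 10% throughout: pooled 85%; last period alone (5% against 10%) 43%.

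The direction of the contrast depends on the shape of the dose response, which the trial does not know in advance.

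**5. The timing statements side by side.** Section 8.2.3 has every man on each dose for 24 weeks. Section 5.2 counts 24 weeks of therapy at a dose for a re-challenged man, which leaves out time off drug. Section 5.9 counts 72 weeks from randomisation. Since 3 × 24 = 72 leaves no slack, a man who loses time and then completes 24 weeks of therapy at the interrupted dose cannot also have 24 weeks on every dose inside 72 weeks.

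**The case against.** The strongest reply is that following the assigned calendar is right. Secondary objective 3 in Section 2.2 concerns the assigned treatments, Section 5.2 invokes intention-to-treat, and comparing arms within a study-week window is protected by randomisation. This stands. A reader might infer that the laboratory comparison is invalid; it is not. The fault lies in calling the window a dose level.

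A reader might also infer that toxicity which led to a hold or reduction is lost. The documents do not support that. The worst grade in the window is used, so an abnormality that triggers a dose change normally counts where it arose; only later samples carry the wrong dose. Nor does every short delay move a level 2 result into level 3, because of the sampling weeks.

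A third tempting step is to make capsules actually taken the main grouping. Dose changes follow toxicity, so men who do not tolerate the drug would leave the three-capsule group and those remaining would look safer. Section 5.2 also warns that the product may stay in tissue for several weeks after stopping, so later abnormalities could be credited to no drug. This objection stands, and such a grouping can only be supplementary.

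Pooling adverse events suits the question of whether the whole regimen is well tolerated. Participant listings are planned in Section 8.2.4, and the monitoring board sets its own report content under Section 8.5. That supports keeping the pooled analysis, but neither provision is a planned comparison by dose step.

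Finally, a reader might infer that the timing of the week-72 endpoint is undefined. Sections 4.4 and 5.9 fix it from randomisation. What remains is a conflict of wording with Sections 5.2 and 8.2.3.

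**Conclusion.** The point holds as one of labelling and omission. Some laboratory results in weeks 25-48 and 49-72 will be reported under a dose the man was not taking, and no planned adverse event comparison can show at which dose step an excess arose. No stated figure is wrong, and the planned comparisons remain valid as comparisons of assigned regimens.

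The size is unknown. The laboratory loss (74% to 61% power at a 15% share) rests on an assumed share and on Section 8.1's rates being placed wholly at the top dose. The adverse event loss (65% to 34%) rests on an excess confined to the last period and on independent periods; with an excess at all doses the pooled analysis is the stronger one. The two analyses answer different questions, and a trial about dose escalation should report both. This is a cheap improvement rather than the repair of an invalid test.

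**What to change.** 1. In Section 8.2.3, keep the calendar-window laboratory comparison as the main randomised analysis and call the windows assigned dose periods.
2. In Section 8.2.4, keep the pooled adverse event analysis and add incidence by arm within each assigned 24-week period of onset. This addition follows assignment, not dose taken.
3. Add supplementary laboratory and adverse event summaries by capsules per day being taken at sampling or onset (0, 1, 2 or 3). Placebo capsules are escalated too, so the grouping can be defined in both arms under the blind. State that it is not protected by randomisation and that drug may persist after stopping.
4. Reconcile the statements on 24 weeks of therapy at a dose (5.2), 24 weeks on each dose level (8.2.3) and 72 weeks from randomisation (5.9). Which dosing rule should apply is for the trial's clinicians.

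The cost is SAP wording, one derived variable and a few more safety tables and comparisons, with less precision within each period. Item 3 depends on what the drug administration form records: the documents mention date of last use and capsule counts, and counts are not collected after stopping, so it should be done as far as those data allow.

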#### **SCHEMA**

**TITLE:** Complementary and Alternative Medicine for Urological Symptoms

(CAMUS).

**DESIGN:** Randomized, double-blind, two arm trial with equal allocation to *Serenoa* 

Repens or placebo.

**POPULATION:** Males  $\geq$ 45 years old with peak urinary flow rate >4 ml/sec, voided volume

>125 ml, AUA symptom score >8 and <24.

**REGIMEN:** Participants will be randomized to one of the treatment arms:

• Serenoa Repens 320 mg once daily for 24 weeks followed by Serenoa Repens 640 mg once daily for 24 weeks followed by

Serenoa Repens 960 mg once daily for 24 weeks.

• Placebo for 72 weeks.

**DURATION:** Participants will continue on study treatment until they meet a protocol

defined reason for treatment discontinuation or complete 72 weeks of

follow-up at the assigned treatment.

**SAMPLE SIZE:** 350 participants randomized in a 1:1 allocation to *Serenoa Repens* or

placebo.

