#### 4.1.1.3 Assessment of all medications

#### 4.1.1.4 Laboratory Tests

- Prostate Specific Antigen (PSA). The PSA measurements will be determined by a central laboratory. Please refer to the manual of operations, Chapter 7, for specimen collection and shipping instructions.
- Urinalysis, including dipstick. If dipstick is positive (greater than 0) for blood or leukocyte esterase, a specimen will be sent for microscopic analysis.
- Complete blood count (CBC), prothrombin time (PT) and serum chemistry profile: serum creatinine, sodium, potassium, chloride, glucose, bicarbonate, ALT (SGPT), AST (SGOT) and GGT.
- Serum for Banking
- 12-lead electrocardiogram (with a copy of the tracing and interpretation stored in the participant's study record). Can be performed at SV1.0 or SV2.0.

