#### 8.0 STATISTICAL CONSIDERATIONS

#### 8.1 Sample size estimation

The primary goal of this study is to determine the efficacy and safety profile of treatment with *Serenoa Repens* compared to placebo. The primary end point of the study is change in AUA symptom score from baseline to 72 weeks. The sample size estimate is based on the following assumptions: a difference in the change in the AUA symptom score from baseline to 72 weeks of 2 points between the placebo arm and the phytotherapy arm, a common standard deviation of the AUA symptom score of 6 points, a two-group t- test, a one-sided significance level of 0.05 and a statistical power of 90%. A one-sided statistical test will be used since an improvement in the AUA symptom score with therapy (i.e., efficacy of therapy) is of primary interest. To detect the hypothesized difference in the change in the AUA symptom score, a sample size of 157 participants per arm will be required. Therefore, a total of 314 participants will be required for the study. To allow for a 10% dropout rate over the course of the study, 350 participants will be recruited to the study.

To determine the power for evaluating safety by measuring hematology and serum chemistry levels, it is assumed that the underlying probability of a severe or life-threatening adverse event detected by laboratory results for placebo is < 2.5%. With 157 participants in each treatment arm, the power to detect a severe or life-threatening adverse event that occurs with frequency  $\ge 10\%$  in the phytotherapy arm at the one-sided 0.05 significance level is 80%.

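### The safety power in section 8.1 does not carry over to the laboratory tests in section 8.2.3, because no participant-level comparison of any grade 3 or greater laboratory abnormality is planned

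*Combined protocol and SAP*

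**What the plan says.** Section 8.1 contains the plan's only safety power calculation. It assumes that "the underlying probability of a severe or life-threatening adverse event detected by laboratory results for placebo is < 2.5" percent. It then says "With 157 participants in each treatment arm, the power to detect a severe or life-threatening adverse event that occurs with frequency" of 10% or more "in the phytotherapy arm at the one-sided 0.05 significance level is 80" percent. One rate is given per arm; no analyte and no dose period is named.

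Section 8.2.3 takes each man's worst grade within each 24-week dose period and then specifies: "For each dose level and laboratory measure, the proportions of participants who have abnormalities of severity grade 3 or greater will be compared", using Fisher's exact test at a two-sided 0.05 level. Section 4.1.1.4 lists the chemistries: "serum chemistry profile: serum creatinine, sodium, potassium, chloride, glucose, bicarbonate, ALT (SGPT), AST (SGOT) and GGT". That is nine analytes. Complete blood counts are graded as well, but their components are not listed.

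Section 8.2.4 covers adverse events over the whole study: "Comparisons of incidence of each adverse event between treatment and placebo will be performed using the two-group chi-square test", or Fisher's exact test where chi-square is unsuitable, with 95% confidence intervals for differences. It also tabulates, by arm, serious adverse events and events causing withdrawal. Section 6.1 counts an abnormal laboratory finding as an adverse event.

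**The concern.** Section 8.1 most naturally describes one event per man: did any laboratory result over the trial reach a severe or life-threatening grade? Section 8.2.3 breaks that event into cells, one per analyte per dose period, and tests each alone. No planned analysis puts the cells back together.

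Tolerability is part of the primary objective in section 2.1, and section 1.1 says the trial is to show whether tolerability merits a long-term study. If severe abnormalities on active treatment fell on several analytes, or at different dose levels in different men, each cell could hold too few men to reach significance even though the overall excess was the one that 8.1 was sized for. A reader of the final report could then set a table of non-significant cells beside the 80% in 8.1 and take more reassurance than the tests can give.

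This is a question of which event is counted. The mismatch between the one-sided level in 8.1 and the two-sided level in 8.2.3 is separate, although it affects the figures below.

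**Working it through.** **Inputs.** From 8.1: placebo rate p0 = 2.5% (the upper end of the stated range), active rate p1 = 10%, n = 157 per arm, one-sided 0.05, stated power 80%. From 8.2.3: two-sided Fisher test at 0.05, one test per measure per dose level. From 4.1.1.4: nine chemistries. Three dose periods.

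**1. Reproduce the stated 80%.** Normal approximation with continuity correction:

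power = Φ{ [ (p1 − p0 − 1/n) − 1.645·√(2p̄(1 − p̄)/n) ] / √[ (p0(1 − p0) + p1(1 − p1))/n ] }, with p̄ = 0.0625.

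- Corrected difference: 0.075 − 1/157 = 0.0686
- Critical value: 1.645·√(2 × 0.0625 × 0.9375/157) = 0.0449
- Standard error: √[(0.0244 + 0.0900)/157] = 0.0270
- Power: Φ[(0.0686 − 0.0449)/0.0270] = Φ(0.88) = 81%

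The 80% is therefore right for one pooled, one-sided comparison.

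**2. The same contrast by exact Fisher test (enumeration, 157 per arm).** Power is 83.5% one-sided and 74.3% two-sided. The 74.3% is what 8.2.3 delivers if every event falls in one analyte and one period.

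**3. What one cell needs.** Two-sided significance requires at least 6 men v 0, 8 v 1 or 10 v 2.

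**4. Number of cells.** 9 × 3 = 27 for the chemistries, plus three for each blood-count component. With an assumed three components, 12 × 3 = 36.

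**5. Spread the same man-level excess over m cells.** Assume an even spread and near-independent cells. The cell rate q solves 1 − (1 − q)^m = 10% (active) or 2.5% (placebo). The chance that any test is significant is 1 − (1 − cell power)^m.

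| m | q active | q placebo | power per cell | any significant |
|---|---|---|---|---|
| 1 | 10% | 2.5% | 74% | 74% |
| 3 | 3.45% | 0.84% | 20% | 48% |
| 6 | 1.74% | 0.42% | 3% | 18% |
| 9 | 1.16% | 0.28% | 0.7% | 6% |

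At m = 9 the expected active-arm count is 157 × 0.0116 = 1.8 men per cell, against the six needed when placebo has none.

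**6. Check on the model.** If each affected man is instead placed in exactly one cell (200,000 simulated trials), the chance of any significant result is 45%, 15% and 5% for 3, 6 and 9 cells. The pattern is the same.

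**7. What 8.2.4 recovers.** One analyte's abnormality recorded as a single adverse event term is compared over all 72 weeks. At 10% v 2.5% this has 81% power by uncorrected chi-square or 74% by Fisher. If the excess falls on several terms, each is still tested alone, and the one-term-per-man figures for 3, 6 and 9 terms are again 45%, 15% and 5%.

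**8. Cost of pooling.** Suppose one analyte has 10% v 2.5% and 11 others each have an assumed background of 0.5% in both arms. Any-of-11 background is 1 − 0.995^11 = 5.4%. The pooled rates become 1 − 0.90 × 0.946 = 14.8% and 1 − 0.975 × 0.946 = 7.7%, and two-sided Fisher power falls to 45%. With 1% background each it is 31%. The single-analyte test keeps 74%.

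**The case against.** **Section 8.1 may mean one specific event.** Its wording is singular: "the power to detect a severe or life-threatening adverse event that occurs with frequency" of 10% or more. On that reading, 8.1 and 8.2.3 agree on the analyte. This is possible, so a reader who infers that the powered event is definitely never tested goes further than the text. The pooled reading is the more natural one, and even the narrow reading names no dose period, whereas 8.2.3 splits the event into three.

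**Laboratory toxicity is not tested only one period at a time.** Sections 6.1 and 8.2.4 together allow a laboratory abnormality to be compared over the whole study. This stands, provided that the abnormality is recorded as a single adverse event term. It largely answers the case of one analyte spread over periods. It does not answer a spread over several analytes.

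**Other safeguards exist.** Serious adverse events and withdrawals are summarized by arm, the Clinical Review Committee reviews all grade 3 to 5 events (6.2, 10.4.3), and the DSMB sees events by arm and grade. These are real oversight. None is a planned between-arm comparison of men with any severe laboratory abnormality, and a grade 3 result need not meet the definition of serious.

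**Even spread is an unfavourable assumption.** This is correct. Men with abnormalities in several analytes or successive periods count in several cells, which raises the power per cell. A reader might infer from the table that spread-out toxicity cannot be detected. The documents do not support that, because the answer depends on a pattern they do not describe.

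**Pooling can hide an organ-specific signal.** This also stands, as step 8 shows. Testing by analyte and dose is a reasonable choice in a dose-escalation trial, and the pooled comparison should not displace it.

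**Conclusion.** The point holds in a limited form. The 80% in 8.1 is correct for a single pooled one-sided comparison, but 8.2.3 and 8.2.4 contain no such comparison, so the figure does not describe the laboratory tests that will be run. Those tests have 74% power when all events sit in one analyte and one period, and about a 48%, 18% or 6% chance of any significant result when the excess is spread over 3, 6 or 9 cells. The last three figures rest on even spread and near-independence; recurrence in the same men would make them higher. All use 2.5% on placebo, and a lower placebo rate would also raise power.

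A reader might also infer that non-significant cells would be declared proof of good tolerability. No section says so; the risk lies in how the tables could be read, not in a stated rule. The gap is worth closing because tolerability belongs to the primary objective and the data needed are already collected.

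**What to change.** - **Section 8.2.3:** add, alongside the analyte-by-period tests and not in place of them, the proportion of men with any grade 3 or greater laboratory abnormality over 72 weeks and within each dose period, by arm, with the difference and its 95% confidence interval.
- **Section 8.1:** define the event, state that the power refers to the 72-week comparison, and give the figure for the test to be used: about 74% for a two-sided Fisher test or 83% one-sided, at 157 per arm.
- **Section 8.2.4:** add a participant-level row for any grade 3 or greater adverse event.

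The cost is a few sentences and table rows from data already scheduled. The one drawback is dilution of the pooled comparison by background abnormalities in unaffected analytes, which is why the analyte-level tests must stay.
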